#### 4 Preparation/Handling/Storage/Accountability

The study device should be handled as per the instruction for use.

Subjects will be asked to return the study device at Visit 3. Sites will account for the return of the study device accordingly, and are expected to dispose/destroy the study device per the standard practice.

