# 9.5 Follow-up of Subjects with Adverse Events

The Investigator is responsible for adequate and safe medical care of subjects during the study and for ensuring that appropriate medical care and relevant follow-up procedures are maintained after the study.

The Investigator should provide the study Sponsor with any new safety information (which includes new AEs and changes to previously reported AEs) that may affect the safety evaluation of the study treatment. For AEs that are unresolved/ongoing at time of subject exit from study, any additional information received at follow-up should be documented in the eCRFs up to study completion (i.e., database lock).

All complaints received after this time period will be considered and processed as spontaneous (following the post-market vigilance procedures) and should be communicated to the study treatment's manufacturer as per local requirements.

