#### 3.3. Key Definitions

**Enrolled subjects** are defined as all subjects who provided signed IC.

**Eligible subjects** are defined as all subjects who provided signed IC and met all the eligibility criteria for this study.

**Baseline** is defined as the last non-missing value prior to the start date of the study treatment. For non-treated subjects, baseline is defined as the value from the Visit 1 (Screening).

**Study Day 1** is defined as the first day of study treatment administration. Study day will be calculated as date of event/collection – first dose date of the study treatment + 1 for all assessments after start of study treatment and as date of event/collection – first dose date of the study treatment for all assessments prior to start of study device use.

End of study date is defined as the date of the latest of the following events:

- Date of early termination collected from the "Subject Disposition" eCRF form (not use if reason for discontinuation is lost to follow-up).
- Last contact date among the following dates (only completed dates) collected on the eCRF:
  - o Subject assessment dates (e.g., IDEEL-SB questionnaire, slit lamp biomicroscopy, BCVA.
  - o AE start and end dates.
  - o Device deficiency dates.
  - o Visit dates (only performed visits).
  - o Study treatment start and end dates.

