#### Derivations:

Length of follow-up (days) = end of study date – date of first dose of study treatment +
 1.

Note: For subjects who are still ongoing in the study at the time of the analysis, the end of study date will be imputed as the data cut-off date.

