#### **Derivations:**

• Treatment duration (days) = date of last dose of study treatment – date of first dose of study treatment + 1.

Note: For treatment duration calculation, if the date of last dose of study treatment is unknown at the time of the analysis, it will be imputed as the end of study date (for subjects who complete or discontinue the study at the time of the analysis) or the data cut-off date (for subjects who are still ongoing in the study).

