#### 6.3.1. Adverse Events

The applicable definition of an AE is in the study protocol. All AEs will be collected from the time of signed IC until study participation is complete. AEs will be coded using the most current available version of the Medical Dictionary for Regulatory Activities (MedDRA) at the time of the data-cut.

All analyses described will be based on treatment-emergent adverse events (TEAEs), if not otherwise specified. TEAEs are those events with onset dates occurring on or after the first dose of study treatment until the end of the study. AEs with an onset date missing will be considered as TEAE.

- **AEs related with study device**: AEs recorded on the AE eCRF page, Relationship to Study Device = Related) and those of unknown relationship (i.e., no answer to the question "Relationship to Study Device").
- **AEs related with test procedure**: AEs recorded on the AE eCRF page, Relationship to Test Procedure = Related) and those of unknown relationship (i.e., no answer to the question "Relationship to Test Procedure").
- Serious adverse events (SAEs): AEs recorded on the AE eCRF page, Was this a Serious Adverse Event? = Yes.
- AEs resulting in study device permanent discontinuation: AEs recorded on the AE
  eCRF page, Action Taken Due To Adverse Event = Study Device Permanently
  Discontinued.
- AEs resulting in death: AEs recorded on the AE eCRF page, Death = Yes or Outcome
   = Fatal.
- Ocular AEs: AEs recorded on the AE eCRF page, Eye = OD or OS.

TEAEs will be summarized as the number and percentage of subjects/eyes by MedDRA Preferred Terms (PT) as an event category. Each subject/eye will be counted only once within a given PT. TEAEs will be displayed in terms of frequency tables sorted on decreasing frequency of PT. In case of equal frequency regarding PT, alphabetical order will be used. In

case any specific TEAE does not have MedDRA PT coded term, it will be summarized under the "Uncoded" category.

The following tables will be created for non-ocular TEAEs (subject-level summary):

- The overall summary table of non-ocular TEAEs will include the number of non-ocular TEAEs and the frequency (number and percentage), and the corresponding 95% CI of subjects with:
  - o Any non-ocular TEAE
  - Any moderate non-ocular TEAE
  - o Any severe non-ocular TEAE
  - Any non-ocular TEAE related with study device
  - Any non-ocular TEAE related with test procedure
  - Any serious non-ocular TEAE

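### The end-of-study date can be set by an AE end date after exit, so length of follow-up, and treatment duration when the last dose is unknown, can run past actual participation

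*SAP*

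**What the plan says.** SAP 3.3 states: "End of study date is defined as the date of the latest of the following events". The first candidate is the early-termination date, which is not used for subjects lost to follow-up. The second is described as "Last contact date among the following dates (only completed dates) collected on the eCRF". Its list covers assessment, device deficiency, visit and treatment dates, and also "AE start and end dates". Nothing limits the result to the exit visit.

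The date is then used in these places:

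- SAP 4.1: "Length of follow-up (days) = end of study date", minus the first-dose date, plus 1.
- SAP 4.6: if the last-dose date is unknown for a subject who completed or discontinued, "it will be imputed as the end of study date".
- SAP Appendix 12.1: a completely missing end date of an AE that is not ongoing is replaced by it.
- SAP 6.3.1: TEAEs run from first dose to the end of the study, which may mean the same date.

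On AE recording, SAP 6.3.1 says: "All AEs will be collected from the time of signed IC until study participation is complete". For AEs unresolved at exit, Protocol 9.5 adds that "any additional information received at follow-up should be documented in the eCRFs up to study completion (i.e., database lock"). On the product, Protocol section 4 says: "Subjects will be asked to return the study device at Visit 3".

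**The concern.** An AE end date is the date an event resolved. It need not be a date on which the subject was still taking part. Under SAP 3.3 as written, an AE that was open at exit and resolved before lock moves that subject's end of study to the resolution date. Subjects without such an AE keep their exit date, so length of follow-up does not measure the same thing in everyone.

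The imputation in SAP 4.6 is harder to defend. It can credit treatment days after the product was due back. For a subject who stopped the device because of an AE and has no recorded last-dose date, treatment would be counted until the AE resolved.

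At stake are two descriptive outputs, the follow-up line in the disposition table and the treatment duration summary. They tell the reader how much observation and exposure lies behind the safety results.

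**Working it through.** The documents state no figure to reproduce here, so the check applies the SAP rules directly.

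**Inputs.** Visit 3 is at Day 30 ±2, that is Day 28 to 32 (Protocol 6.1; SAP Table 2). There are 54 evaluable and 68 enrolled subjects (Protocol 6.1 and 6.4.1). The aqueous deficient group has 12 evaluable (Protocol synopsis) and 15 enrolled (Protocol 6.1). The lag L from exit to the recorded AE end date is an assumption. It cannot exceed the time from exit to database lock, which the documents do not give. I show 7, 14, 30 and 60 days.

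**Formula.** End of study = max(exit date, AE end date). Length of follow-up = end of study − first dose + 1, which equals exit day + L. Treatment duration takes the same value, but only if the last-dose date is unknown.

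| Exit day | Actual | L = 7 | L = 14 | L = 30 | L = 60 |
|---|---|---|---|---|---|
| Day 30 | 30 | 37 | 44 | 60 | 90 |
| Day 10 (early exit) | 10 | 17 | 24 | 40 | 70 |

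**Shift in the mean from one affected subject (L/n).**

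- Overall, L = 14: 14/68 = 0.21 to 14/54 = 0.26 day.
- Overall, L = 30: 30/68 = 0.44 to 30/54 = 0.56 day.
- Overall, L = 60: 60/68 = 0.88 to 60/54 = 1.11 days.
- Aqueous deficient group, L = 14: 14/15 = 0.93 to 14/12 = 1.17 days.
- Aqueous deficient group, L = 30: 30/15 = 2.0 to 30/12 = 2.5 days.
- Aqueous deficient group, L = 60: 60/15 = 4.0 to 60/12 = 5.0 days.

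**SD and maximum.** If everyone else has exactly 30 days, one affected subject gives a sample SD of L/√n. With n = 54 that is 14/√54 = 1.9 days or 60/√54 = 8.2 days, where it would otherwise be 0. The maximum becomes 44 or 90 days instead of 30.

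**How many subjects.** At the planned AE proportion of 0.0543 (Protocol 6.4.1), 0.0543 × 54 = 2.9 and 0.0543 × 68 = 3.7 subjects would have any AE. This is an upper-end illustration. Only those whose AE is ongoing at exit and gets a complete end date before lock are affected, and the documents give no figure for that.

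**TEAE counts.** AE start dates are in the same maximum as AE end dates. A complete onset date is therefore never later than that subject's own end-of-study date, and a late AE end date admits no event that would otherwise be excluded. An AE with a wholly missing onset date is a TEAE by rule.

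**With both durations ended at exit.** A completer seen within the window gets 28 to 32 days, and a Day 10 exit gets 10 days.

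**The case against.** Four arguments stand against this point.

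- The SAP calls this component a last contact date, and counting follow-up to the last recorded information is a definable choice. That is fair for follow-up in general. It does not justify a clock that runs longer only for subjects with an AE open at exit, and it does not justify imputing treatment to that date.
- Post-exit end dates may be rare. Protocol 9.5 concerns information that happens to be received, and Protocol 7.4 requires no specific follow-up procedures. This stands: such dates are possible, but nothing shows they are common.
- Treatment duration uses the actual last-dose date when it is known. Treatment end dates are on the eCRF, dosing is recorded daily in a diary, and the product is returned at Visit 3. This also stands. An error needs an AE open at exit, a complete later end date entered before lock, and an unknown last dose, all in one subject.
- A simple cap on the shared date could do harm. Protocol 9.5 also asks for new AEs as safety information. If the TEAE window closed at exit, a recorded AE with later onset would drop out of the AE tables and of Listing 16.2.5.1, which cover TEAEs only. This stands and shapes the fix.

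A reader might also infer that TEAE windows differ between subjects in a way that changes counts, or that exposure is overstated in the safety analysis generally. The documents do not support either. Start dates are in the same maximum, no exposure-adjusted rate is planned, and AE results are numbers and percentages of subjects or eyes. The AE end dates imputed under Appendix 12.1 feed no planned AE-duration table.

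**Conclusion.** The point holds for two descriptive outputs and is minor. Length of follow-up can exceed participation for subjects whose AE is ongoing at exit and gets a complete end date before lock. Treatment duration is affected only if the last-dose date is also unknown. One subject with a 14- to 60-day lag moves the overall mean by about 0.2 to 1.1 days, with larger effects on the maximum, the SD and the small dry eye groups. The lags are assumptions, and 60 days is at the upper end of what is shown. AE percentages, TEAE counts, the IDEEL-SB endpoint, BCVA, biomicroscopy and device deficiencies are not affected.

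**What to change.** In SAP 4.1 and 4.6, define a separate end-of-participation date: the Visit 3 or early-exit date or, for subjects lost to follow-up, the last performed visit or contact. Exclude AE end dates from it. Use it for length of follow-up and for imputing an unknown last-dose date.

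Leave the SAP 3.3 date unchanged for TEAE classification, so that no recorded AE leaves the TEAE tables and listings.

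The change is about two lines of SAP text and needs no new data. The price is that the SAP then carries two end dates, so they need distinct names and each derivation must say which one it uses.

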## 3.4. Missing Data

Unless otherwise specified in this SAP, all data will be evaluated as reported in the database and no imputation for missing values will be done, except for AEs dates. Handling of partial dates is described in Appendix 13.1.

# 3.5. Analysis Visit Windows

As per the protocol, data will be collected for the assessments at the Screening/Baseline (Visit 1), 15-day Follow-up (Visit 2), and 30-day/Exit (Visit 3). The data will be collected within  $\pm 2$ 

days window for the Visit 2 and Visit 3. By-visit summaries will use the analysis visit. Scheduled, unscheduled and early termination visits will be windowed based on the following analysis visit window (Table 2).

- 1) If the scheduled records do not fall within a visit window, then the records will be flagged as out of the allowed window and the original visit from the eCRF will be assigned for the analysis visit. In case of unscheduled records not falling within a visit window, the original visit from the eCRF will be assigned.
- 2) For post-baseline visits, if there is more than 1 record available within the same visit window, the following rules will be applied:
  - a. Select the record collected at the scheduled visit.
  - b. If there are no records at the scheduled visit, then the record closest to the target day will be used.
  - c. If there are multiple records with the same distance to the target day, the latest record will be used.
- For Baseline visit, the last non-missing record among scheduled and unscheduled assessments will be selected.

Table 2: Analysis Visit Window

Analysis	Target Study	Visit Window for , IDEEL-SB, BCVA,	
Visit	Day	Biomicroscopy	
Baseline	1	<=1	
Visit 2	15	13 to 17	
Visit 3	30	28 to 32	

In general, only observations assigned to an analysis visit window will be included in the analysis. Data collected at unscheduled visits will be included in the data listings. In addition, any data collected out of the allowed window will be flagged in the listings.

# 3.6. Pooling of Centers

Summaries will be provided pooled for all sites overall and by DED group if not indicated otherwise.

# 4. Subject Characteristics

# 4.1. Subject Disposition

Summary table reflecting subject disposition will present:

- Number of enrolled subjects (only for overall).
- Number of non-eligible subjects (any eligibility criteria not met) [only for overall].
- Number of subjects by reason for ineligibility (only for overall): inclusion criteria not met; exclusion criteria met.
- Number (%) of eligible subjects.
- Number (%) of subjects who completed the study.
- Number (%) of subjects who discontinued the study with reasons for early study termination.
- Length of follow-up (days).
- Number (%) of subjects included in each analysis set (FAS and PP).

Supportive listings will be provided for subject disposition and study visits.

#### Derivations:

Length of follow-up (days) = end of study date – date of first dose of study treatment +
 1.

Note: For subjects who are still ongoing in the study at the time of the analysis, the end of study date will be imputed as the data cut-off date.

#### 4.2. Protocol Deviations

Analysis Set: FAS

Protocol deviations will be identified periodically throughout the study based on the "Protocol Deviation Criteria Form". This form is transferred before each analysis indicating subject with protocol deviations as reason of exclusion from PP. Major protocol deviations that lead to the exclusion from PP will be summarized. All protocol deviations will be listed.

# 4.3. Demographics and Clinical Characteristics at Baseline

Analysis Set: FAS

Demographic and clinical characteristics at Baseline will be summarized using the information collected from the screening data. Demographic characteristics will include:

- Age (years).
- Age categories: >=18 years to <30 years, >=30 years to <50 years, >=50 years to <70 years and >=70 years.
- Sex: Male, Female, Unknown, Unconfirmed.
- Race: American Indian or Alaska Native, Asian, Black or African American, Native Hawaiian or other Pacific Islander, White, Other, Unknown, Unconfirmed.
  - Note: An additional category "Mixed" will be created for subjects with more than one race reported.
- Ethnicity: Hispanic or Latino, Not Hispanic or Latino, Unknown, Unconfirmed.
- IDEEL-SB symptoms score.
- \_
- BCVA score (logMAR) [eye-level summary].

A supportive listing for demographic and clinical characteristics will be provided.

# 4.4. Targeted Medical History

Medical conditions within 1 year prior to the Screening/Baseline (Visit 1) will be collected from "Targeted Medical History and Concomitant Medication" eCRF form.

Any preexisting medical conditions or signs/symptoms present in a subject prior to the start of the study (i.e., before IC is signed) are not considered AEs in the study and should be recorded in the Medical History section of the eCRF.

A supportive listing for medical history will be provided.

# 4.5. Targeted Concomitant Medication

Concomitant medications taken within the past 30 days prior to the Screening/Baseline (Visit 1) will be listed.

#### 4.6. Treatment Duration and Missed Doses

Systane Complete PF will be administered as shown in Figure 2.

The frequency (number and percentage) of subjects with at least one missed dose during the study and the treatment duration (in days) will be summarized.

#### **Derivations:**

• Treatment duration (days) = date of last dose of study treatment – date of first dose of study treatment + 1.

Note: For treatment duration calculation, if the date of last dose of study treatment is unknown at the time of the analysis, it will be imputed as the end of study date (for subjects who complete or discontinue the study at the time of the analysis) or the data cut-off date (for subjects who are still ongoing in the study).

# 5. Efficacy Analysis Strategy

This study defines one primary effectiveness endpoint

The FAS will be used for all effectiveness analyses. The PP population will be the supportive analysis set for primary and supportive effectiveness analyses.

All endpoints will be summarized overall and by DED groups.

No imputation for missing values will be carried out for the primary effectiveness analyses.

# 5.1. Efficacy Endpoints

#### PRIMARY EFFECTIVENESS ENDPOINT:

The primary effectiveness endpoint is the IDEEL-SB score at Baseline and at Visit 3.

## SUPPORTIVE EFFECTIVENESS ENDPOINTS:

# **5.2.** Efficacy Hypotheses

There are no statistical hypotheses in this study. Data on primary effectiveness endpoints will be summarized using descriptive statistics.

# 5.3. Statistical Methods for Efficacy Analyses

#### 5.3.1. Primary Effectiveness

[figure not shown]
DES will be assessed using the IDEEL-SB questionnaire (see Appendix 13.2) at the Screening/Baseline visit (Day 1) before Systane Complete PF use, and at Visit 3 (and at unscheduled and at early exit visits, as necessary).

The primary effectiveness endpoint is the IDEEL-SB score. The IDEEL-SB score is calculated by the mean value of the non-missing item scores multiplied by 25

The primary effectiveness endpoint will be summarized as a continuous variable at each analysis visit (Baseline and Visit 3). The mean IDEEL-SB score will be presented together with the corresponding 95% CI. In addition, the change from Baseline will be summarized at Visit 3.

#### Derivation:

• IDEEL-SB score = (Sum of (Item 1,..., Item 20) / n) x 25, where n = number of items with non-missing answer.

# 5.4. Handling Missing Data

Missing data for primary and supportive effectiveness endpoints will not be imputed. The IDEEL-SB score is calculated if at least 50% (10 items) of the 20 items within the dimension are completed (non-missing), otherwise the score is set to missing.

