#### 6 STUDY DESIGN

# 6.1 Overview of Study Design

This is a post-market, multicenter, non-comparative, single arm, open-label, prospective clinical study.

The study will be conducted in the US and/or outside the US, where the product is commercially available, in clinical sites known to routinely manage patients with DED. The overall study duration (first subject screened to last subject's final study visit) is expected to be approximately 2 months.

Subjects will be enrolled into the study after signing the informed consent form (ICF).

Subjects who meet all of the inclusion criteria and none of the exclusion criteria will initiate

[figure not shown]
treatment with Systane Complete PF. On Day 1, eligible study participants will be asked to instill one drop of Systane Complete PF in each eye on-site (during the Screening/Baseline visit) and the subsequent drop only after 8 hours ( $\pm$  1 hour) at home. For the rest of the study duration (up to Visit 3), subjects will be asked to self-administer 1-2 drops in each eye; four times a day. The dose selected in this study is the dose approved for Systane Complete PF for the management of DED.

Subjects will participate in the study for approximately 30 days, with a phone call scheduled on Day  $15 \pm 2$  (Visit 2) and a follow-up visit scheduled on Day  $30 \pm 2$  (Visit 3). Subjects may have unscheduled visits if deemed necessary per the Investigator's judgment.

Subjects will be asked to complete patient questionnaires on Day 1 (Impact of Dry Eye on Everyday Life - Symptom Bother [IDEEL-SB] and at Visit 3 (IDEEL-SB). In addition, subjects will be instructed to document Systane Complete PF dosing information on a daily basis using a subject diary.

[figure not shown]
A summary of the study design is shown in Figure 1. Systane complete preservative-free dose regimen is shown in Figure 2. Study assessments are shown in the Schedule of Assessments (Table 4).

The study will enroll approximately 68 subjects with the objective of 54 subjects completing treatment with Systane Complete PF. Investigators will be asked to enroll approximately 22% of subjects with aqueous deficient dry eye (i.e., 15 subjects), 45% of subjects with evaporative dry eye (i.e., 31 subjects), and 33% of subjects with mixed dry eye (i.e., 22 subjects) as per the Tear Film and Ocular Surface Society (TFOS) Dry Eye Workshop (DEWS) II criteria for DED stratification.

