#### 6.4.1 Sample Size

The study will recruit 68 subjects with a target to complete 54 evaluable subjects.

With a sample size of 54, a two-sided 95% confidence interval for a single proportion will extend 0.060 from the observed proportion when the expected proportion is 0.0543 (AEs).

Table 2 presents the precision for various rates of categorical outcomes.

**Table 2.** Precision for Various Percentages

Comple Size	Precision (%) for Various Rates of Outcomes				
Sample Size	5%	10%	25%	50%	
54	5.81%	8.00%	11.55%	13.34%	

Precision calculated according to a simple asymptotic formula for a 2-sided 95% confidence interval for a proportion based on the normal approximation of the binomial distribution.

Investigators will be asked to enroll approximately 22% of subjects with aqueous deficient dry eye, 45% of subjects with evaporative dry eye, and 33% of subjects with mixed dry eye as per the TFOS DEWS II criteria.

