#### 6.4.6 Exit / Discontinuation Criteria

Participation of a subject in this clinical study may be discontinued for any of the following reasons:

- Screen failure
- AE/serious adverse event (SAE)
- Death
- Lack of efficacy
- Lost to follow-up
- Physician decision
- Protocol violation
- Study terminated by Sponsor or regulatory authority
- Technical problems with the study device
- Withdrawal by subject

If a subject withdraws prematurely from the study due to the above criteria or any other reason, study staff should make every effort to complete the full panel of assessments scheduled for the Early Exit Visit. The reason for subject withdrawal must be documented in the eCRF.

In the case of subject lost to follow-up, attempts to contact the subject must be made and documented in the subject's medical records. Withdrawn subjects will not be replaced.

A subject will be considered lost to follow-up if he or she fails to return for scheduled visits and is unable to be contacted by the study site staff. The following actions must be taken if a subject fails to return to the clinic for a required study visit:

- The site will attempt to contact the subject and reschedule the missed visit as soon as possible and counsel the subject on the importance of maintaining the assigned visit schedule and ascertain if the participant wishes to and/or should continue in the study.
- Before a participant is deemed lost to follow-up, the Investigator or designee will make
  every effort to regain contact with the subject (where possible, 3 telephone calls and, if
  necessary, a certified letter to the subject's last known mailing address or local equivalent
  methods). These contact attempts should be documented in the subject's medical record or
  study file.
- Should the subject continue to be unreachable, he or she will be considered to have withdrawn from the study with a primary reason of lost to follow-up.

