#### For reporting conventions:

- The number of non-missing and missing observations will be presented as whole numbers.
- The minimum and maximum will be presented with the same number of decimal places as presented in the data.
- The mean (and correspondent 95% CI), median, Q1 and Q3 will generally be displayed with one more decimal place than presented in the data.
- The SD will generally be displayed with 2 more decimal places than the raw data. If there is only one observation (n=1), the SD will be displayed as a hyphen ("-").
- If there is no observation, summary statistics will be displayed with a hyphen ("-").

Qualitative variables will be summarized by frequency counts (n) and percentages (%). Unless otherwise stated, the calculation of proportions/percentages for a given qualitative variable will exclude subjects/eyes with missing values from the denominator.

For reporting conventions, percentages will be reported to one decimal place unless greater precision is deemed appropriate, except for cases when 100% is presented. In cases of a count of 0, the percentage will not be presented.

In case the analysis refers only to certain visits/timepoints, summary statistics and percentages will be based on the number of subjects/eyes having available result at each visit/timepoint. Summaries on change from Baseline by visit/timepoint will be based on subjects/eyes who have both baseline and post-baseline values at the visit/timepoint being summarized.

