## 8. Sample Size and Power Calculations

The study will recruit 68 subjects with a target to complete 54 evaluable subjects.

With a sample size of 54, a two-sided 95% CI for a single proportion will extend 0.060 from the observed proportion when the expected proportion is 0.0543 (AEs). Table 3 presents the precision for various rates of categorical outcomes.

Table 3: Precision for Various Percentages

Sample Size	Pro	ecision (%) for V	arious Rates of Outo		
Sample Size	5%	10%	25%	50%	
54	5.81%	8.00%	11.55%	13.34%	

Precision calculated according to a simple asymptotic formula for a 2-sided 95% CI for a proportion based on the normal approximation of the binomial distribution.

Investigators will be asked to enroll approximately 22% of subjects with aqueous deficient DE, 45% of subjects with evaporative DE, and 33% of subjects with mixed DE as per the Tear Film and Ocular Surface Society (TFOS) Dry Eye Workshop (DEWS) criteria.

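### The FAS result for IDEEL-SB change covers only subjects with a Visit 3 score, and no visible analysis checks what the missing scores do to it

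*SAP*

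**What the plan says.** Protocol 8.1 and SAP 2.1 define the FAS as all subjects with at least one dose and make it the primary set for effectiveness.

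SAP 5.1 words the endpoint by visit: "The primary effectiveness endpoint is the IDEEL-SB score at Baseline and at Visit 3". SAP 5.3.1 summarises the score at each of the two visits and adds the change from Baseline at Visit 3. The reporting conventions in SAP 3.2 restrict that change: "Summaries on change from Baseline by visit/timepoint will be based on subjects/eyes who have both baseline and post-baseline values at the visit/timepoint being summarized".

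SAP 5.4 says: "Missing data for primary and supportive effectiveness endpoints will not be imputed". Protocol 8.2 also rules out imputation, without exception.

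Protocol 6.4.6 lists adverse events and "Lack of efficacy" among the exit reasons and does not replace withdrawn subjects. It asks sites to try to complete the early-exit assessments, and the schedule of assessments allows IDEEL-SB there as necessary. Under SAP 3.5 a score counts as Visit 3 if it falls on Day 28 to 32, or if it falls outside every window but carries the Visit 3 label on the eCRF.

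SAP 13 lists two IDEEL-SB summary tables, one on the FAS and one on the PP set.

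**The concern.** A reader who sees a change labelled FAS will take it to describe everyone who was treated. It describes only those with a usable Visit 3 score. When poor response or intolerance is a recognised reason to leave, the subjects without that score may well be those who improved least.

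In a randomised trial a similar loss in the control arm might offset part of this. Here there is one arm, no hypothesis test and no threshold. The mean change and its confidence interval are the performance result, so any selective loss goes straight into them.

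The PP table cannot serve as the check. PP is a subset of the FAS, so it removes further subjects and restores none.

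**Working it through.** **The plan's own figure.** Protocol 6.4.1 states: "With a sample size of 54, a two-sided 95% confidence interval for a single proportion will extend 0.060 from the observed proportion", at an expected proportion of 0.0543. The Wald half-width is 1.96 × sqrt(0.0543 × 0.9457 / 54) = 0.0604, which agrees. The precision table (5.81%, 8.00%, 11.55%, 13.34%) also reproduces. These figures concern proportions. The documents give no expected mean or SD for the IDEEL-SB change.

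**How much loss is planned.** SAP 8: "The study will recruit 68 subjects with a target to complete 54 evaluable subjects". Protocol 6.1: "The study will enroll approximately 68 subjects with the objective of 54 subjects completing treatment with Systane Complete PF". The difference is 68 − 54 = 14, and 14/68 = 20.6%. Neither document calls the 14 dropout. SAP 3.3 says enrolled subjects "are defined as all subjects who provided signed IC", and Protocol 6.4.6 lists screen failure as an exit reason. Screen failures therefore sit inside the 68, but they are not dosed and so are outside the FAS. With s screen failures, the FAS is 68 − s and the planned loss from it is (14 − s)/(68 − s). This is largest, at 20.6%, when s = 0.

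**Effect on the mean change.** Let D be the mean improvement in subjects with Visit 3 scores, L the mean improvement in dosed subjects without one, and c and m the two counts. The mean over all dosed subjects is (c × D + m × L)/(c + m). If L = 0 (an assumption), the reported change exceeds that mean by the fraction (c + m)/c − 1, which equals 1/(1 − d) − 1 for a loss fraction d = m/(c + m). Taking c = 54:

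| Screen failures among the 14 | FAS | No Visit 3 score | Loss from FAS | Excess if L = 0 |
|---|---|---|---|---|
| 0 | 68 | 14 | 20.6% | 68/54 − 1 = 25.9% |
| 4 | 64 | 10 | 15.6% | 64/54 − 1 = 18.5% |
| 7 | 61 | 7 | 11.5% | 61/54 − 1 = 13.0% |
| 10 | 58 | 4 | 6.9% | 58/54 − 1 = 7.4% |
| 14 | 54 | 0 | 0% | 0% |

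By loss fraction alone: 5% loss gives 1/0.95 − 1 = 5.3%, and 10% loss gives 1/0.90 − 1 = 11.1%.

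**In points, for an assumed D = 10.**
- L = 0: the all-dosed mean is 540/68 = 7.9 with 14 missing, or 540/61 = 8.9 with 7 missing.
- L = −5 (those lost worsened): (540 − 70)/68 = 6.9, or (540 − 35)/61 = 8.3.
- L = 10 (those lost improved as much as the rest): 10.0 in both cases, so no bias.

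**The case against.** *The plan does not provide for 21% dropout.* A reader might infer that it does from 68 and 54. The documents do not support that. Eligibility depends on an IDEEL-SB score taken at the same visit as consent, so some of the 14 may be screen failures, who cannot bias the FAS. This objection stands: 20.6% and 25.9% are upper bounds under the planned numbers.

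*The paired change is already planned.* This also stands. A reader might infer from the endpoint wording that the result is a difference of two unpaired means, which loss alone could move. If those lost started 5, 10 or 15 points higher than those who stayed, the visit means would differ by 0.206 × 5, 10 or 15 = 1.0, 2.1 or 3.1 points with nobody improving. But SAP 3.2 and 5.3.1 provide a paired change, which that mechanism does not touch. The shift affects only the two visit means shown side by side, and the 5 to 15 points are illustrative.

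*The loss will be visible.* In part. Every continuous summary shows n, the disposition table gives exit reasons, and missed visits are listed. The table shells are a separate document, and the supportive-endpoint text is blacked out, so a relevant summary there cannot be excluded. But counts do not show whether those without Visit 3 scores differ at Baseline or how they were doing when they left.

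*Early-exit scores will fill the gap.* Some should exist. A score that SAP 3.5 does not assign to Visit 3 does not enter the Visit 3 change, and a dosed subject with no post-baseline score is absent under any windowing rule.

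*The study is descriptive.* True, so no test or decision rule can flip. The effect is on the estimate and its interval.

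**Conclusion.** The concern holds in this form: the primary IDEEL-SB change is an available-case estimate under an FAS label, outcome-related exit is foreseeable from the protocol, and no visible analysis examines the effect of missing Visit 3 scores. Improvement can be overstated. That it will be overstated is a stronger reading that the documents do not support, because the direction depends on those who leave improving less than those who stay.

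Under the planned numbers the overstatement runs from 0% (all 14 are screen failures) to 25.9% (all 14 are lost after dosing), and is about 13% if they split evenly. These figures assume zero change in those lost and a Visit 3 score for each of the 54. They would be larger if those lost worsened and smaller if they improved. The point is worth settling before database lock. It does not invalidate the study.

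**What to change.** 1. In SAP 5.1 and 5.3.1, make the paired change from Baseline to Visit 3 the lead primary summary, with the Baseline mean of the same paired subjects beside it.
2. In SAP 5.4, keep the primary table unimputed. Add a table of n, exit reason and Baseline IDEEL-SB score for FAS subjects with and without a Visit 3 score.
3. Add one labelled supportive summary of change from Baseline to the last observed post-baseline IDEEL-SB score, including early-exit scores whatever their study day. It uses observed values only. State how many FAS subjects have no post-baseline score.
4. Optionally, add a row that gives zero change to subjects with no post-baseline score. This is imputation, so label it as sensitivity only and reconcile it with the statement in Protocol 8.2 that rules imputation out. Its interval will be too narrow, and zero change is not conservative if those subjects worsened.

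Items 1 to 3 need SAP wording, one extra table and one extra summary. They need no new data collection beyond the early-exit assessments already requested. The downside is a little more analysis and possibly a less favourable supportive figure. If loss proves small, the supportive summary will agree closely with the primary one.
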